Appendix 14 Table of Topical Corticosteroid Potencies

Category	Drug	Formulation
Ultra High (I)	Clobetasol proprionate	Cream 0.05% Ointment 0.05% Lotion 0.05%
	Fluocinonide	Cream 0.1%
	Diflorasone diacetate	Ointment 0.05%
	Halobetasol proprionate	Cream 0.05% Ointment 0.05%
High (II)	Amcinonide	Ointment 0.1%
	Betamethasone dipropionate	Ointment 0.05%
	Desoximetasone	Cream 0.05% Ointment 0.05%
	Fluocinonide	Cream 0.05% Ointment 0.05%
	Halcinonide	Cream 0.1% Ointment 0.1%
High (III)	Betamethasone dipropionate	Cream 0.05%
	Betamethasone valerate	Ointment 0.1%
	Dicflorasone diacetate	Cream 0.05%
	Triamcinolone acetonide	Ointment 0.1%
Moderate (IV and V)	Betamethasone dipropionate	Lotion 0.02%
	Betamethasone valerate	Cream 0.1% Lotion 0.1%
	Desoximetasone	Cream 0.05%
	Fluocinolone acetonide	Cream 0.025% Ointment 0.025%
	Fluticasone proprionate	Cream 0.05%
	Fludroxycortide	Ointment 0.05%
	Hydrocortisone butyrate	Ointment 0.1% Cream 0.1%
	Hydrocortisone probutyrate	Cream 0.1%
	Hydroxycortisone valerate	Cream 0.2% Ointment 0.2%
	Mometasone furoate	Cream 0.1% Ointment 0.1%
	Triamcinolone acetonide	Cream 0.025% Lotion 0.025% Cream 0.1% Lotion 0.1%

Category	Drug	Formulation
Low (VI)	Betamethasone valerate	Lotion 0.05%
	Desonide	Cream 0.05% Ointment 0.05% Lotion 0.05%
	Fluocinolone acetonide	Cream 0.01%
Low (VII)	Dexamethasone sodium phosphate	Cream 0.1%
	Hydrocortisone	Cream 1% Lotion 1% Ointment 1% Cream 2.5% Lotion 2.5% Ointment 2.5%
	Hydrocortisone acetate	Cream 1%
	Methylprednisolone acetate	Cream 0.25%

**List of Abbreviations**

Definition	Abbreviation
Analysis Of Covariance	ANCOVA
Anatomical-Therapeutic-Chemical	ATC
Asthma Control Questionnaire	ACQ-5
Atopic Dermatitis	AD
Atopic Dermatitis Sleep Scale	ADSS
Body Mass Index	BMI
Body Surface Area	BSA
Confidence Interval	CI
Dermatology Quality Of Life Index	DLQI
Eczema Area Severity Index	EASI
Electrocardiogram	ECG
Electronic Case Report Forms	eCRF
Electronic Diary	e-Diary
Full Analysis Set	FAS
Inflammatory Bowel Disease	IBD
Last Observation Carried Forward	LOCF
Least Square	LS
Markov Chain Monte Carlo	MCMC
Medical Dictionary For Regulatory Activities	MedDRA
Missing Not At Random	MNAR
Multiple Imputation	MI
Orally Once Daily	QD
Pain Numeric Rating Scale	Pain NRS
Patient Global Assessment	PtGA
Patient-Oriented Eczema Measure	POEM
Peak Pruritus Numerical Rating Scale	PP-NRS
Per-Protocol	PP
Pharmacodynamic	PD
Pharmacokinetic	PK
Preferred Term	PT
Scoring Atopic Dermatitis	SCORAD
Statistical Analysis Plan	SAP
System Organ Class	SOC
Table, Listing And Figures	TLF
Treatment Failure	TF
Treatment-Emergent AEs	TEAE
Tuberculosis	TB
Validated Investigator Global Assessment	vIGA
Visual Analog Scale	VAS
World Health Organization Drug Dictionary	WHO-DD

## I. Introduction

### A. Background

RPT193-02 is designed to assess the efficacy and safety of multiple dose levels of RPT193 in subjects with moderate-to-severe atopic dermatitis (AD). This randomized, double-blind, placebo-controlled study will compare 3 dose levels of RPT193 to placebo with a treatment duration of 16 weeks. Investigational product will be administered as monotherapy for AD in adult subjects who have had an inadequate response to topical medications for AD (e.g., corticosteroids) or who are otherwise unable to take topical medications. Maximum clinical benefit in the 4-week Phase 1b (RPT193-01) trial was observed 2 weeks after cessation of treatment and suggested that RPT193 may have therapeutic effects beyond the dosing period. Thus, after completion of treatment at 16 weeks, subjects will continue to be followed for an additional 8 weeks to understand whether further improvement in clinical parameters and/or sustained responses are observed beyond the treatment period. The data generated during the current study will contribute to efficient and appropriate design of future clinical studies, including pivotal studies with RPT193 in subjects with AD.

The protocol for Study RPT193-02 describes the general approach to analysis of data from the study. This analysis plan describes additional details needed to complete such an analysis.

### B. Statistical Analysis Plan Scope

This Statistical Analysis Plan (SAP) is based on Protocol RPT193-02 Amendment v2.0. (dated 07 July 2023) and electronic Case Reports Form (eCRF) casebook version 4.0.

This SAP will govern the analysis of data from this study. The plan may be modified until the time of treatment unblinding. Any deviations from the analysis plan, including any after the time of treatment unblinding, will be documented as such in the study report.

The analyses for the pharmacokinetic (PK) data will be described in a separate analysis plan. The analysis for pharmacodynamic (PD) and biomarkers will not be included in this SAP and will be described in a separate analysis plan.

### C. Changes to Planned Analyses from Protocol

The following changes or additions to the planned analyses described in the protocol are noted:

- In Protocol Amendment v2.0, the randomization list is stratified based on region (North America vs. rest of world), baseline vIGA scores (vIGA of 3 vs. 4), and prior dupilumab or tralokinumab use (yes or no). It was later determined that no subjects will be recruited from rest of the world, and therefore stratifying by region in randomization will no longer be required. The existing randomization master list including region as a stratification factor will not be modified or replaced. Any strata related to rest of world region will be disregarded by the IWRS in assigning randomized treatment. All statistical analyses will be adjusted to align with this change by removing region as a stratification factor as applicable.
- Subgroup analysis by pretreatment CCL17/22 levels as required by the protocol is

[REDACTED] ( [REDACTED] ) not included in this SAP. This analysis will be covered by a separate analysis plan for PD data.

## II. Protocol Objectives and Study Endpoints

Objectives	Endpoints
Primary	

To evaluate the efficacy of RPT193 administered orally once daily (QD) for 16 weeks to subjects with moderate-to-severe AD.

	

% change in Eczema Area Severity Index (EASI) from baseline at Week 16.

To evaluate the safety and tolerability of RPT193 administered orally QD for 16 weeks.

	

Incidence of treatment-emergent adverse events.

Key Secondary	

 
To evaluate the efficacy of RPT193 administered orally QD for 16 weeks to subjects with moderate-to-severe AD.
 
	
 
% of subjects achieving a Validated Investigator Global Assessment (vIGA) score of 0 or 1 at Week 16.
 
% of subjects achieving EASI-75, defined as a 75% reduction in EASI from baseline to Week 16.
 

 
To evaluate the efficacy of RPT193 administered orally QD for 16 weeks to subjects with moderate-to-severe AD on subject reported symptoms associated with AD. Itch peak pruritus numerical rating scale (PP-NRS).
 
	
 
% change from baseline in PP-NRS from an itch daily e-Diary at Week 16.
 

Secondary	

 
To evaluate the efficacy of RPT193 administered orally QD for 16 weeks to subjects with moderate-to-severe AD.
 
To evaluate the efficacy of RPT193 administered orally QD for 16 weeks to subjects with moderate-to-severe AD on subject reported symptoms associated with AD.
 
	
 
% of subjects achieving EASI-50, defined as a 50% reduction in EASI from baseline to Week 16.
 
% of subjects achieving EASI-90, defined as a 90% reduction in EASI from baseline to Week 16.
 
% of subjects achieving at least 2-point reduction in vIGA score from baseline to Week 16.
 
% of subjects achieving EASI-75 from baseline to Week 2, 4, 8, and 12.
 
% of subjects achieving EASI-50 from baseline to Week 2, 4, 8, and 12.
 
% of subjects achieving EASI-90 from baseline to Week 2, 4, 8, and 12.
 
% of subjects achieving at least 2-point reduction in vIGA score from baseline to Week 2, 4, 8, and 12.
 
Time to achieving EASI-75 from baseline.
 
Time to achieving EASI-50 from baseline.
 
Time to achieving EASI-90 from baseline.
 
Change from baseline PP-NRS from an itch daily electronic Diary (e-Diary) at Week 16.
 
For subjects with baseline PP-NRS <math>\geq 4</math>:             
 
% of subjects achieving <math>\geq 4</math>-point reduction in PP-NRS from baseline at Week 2, 4, 8, 12, and 16.
 
Time to achieving <math>\geq 4</math>-point reduction in PP-NRS from baseline.
 
 
 
For subjects with baseline PP-NRS <math>\geq 3</math>:             
 
% of subjects achieving <math>\geq 3</math>-point reduction in PP-NRS from baseline at Week 2, 4, 8, 12, and 16.
 
Time to achieving <math>\geq 3</math>-point reduction in PP-NRS from baseline.
 
 
 

Exploratory (Clinical)	

 
To evaluate the clinical efficacy of RPT193 administered orally QD for 16 weeks to subjects with moderate-to-severe AD.
 
	
 
% change in SCORing Atopic Dermatitis (SCORAD) from baseline at Week 2, 4, 8, 12, and 16.
 
% change in Body Surface Area (BSA) of AD affected AD from baseline at Week 2, 4, 8, 12, and 16.
 


 
To evaluate the efficacy of RPT193 administered orally QD for 16 weeks to subjects with moderate-to-severe AD on subject reported symptoms associated with AD.
 
	
 
Change from baseline to Week 16 in:             
 
Sleep quality (visual analog scale [VAS] from SCORAD)
 
Patient-oriented eczema measure (POEM)
 
Dermatology Quality of Life Index (DLQI)
 
Skin pain NRS
 
Patient global assessment (PtGA).
 
Atopic dermatitis sleep scale (ADSS)
 
 
 
Asthma Control Questionnaire (ACQ-5) (in subjects with a history of asthma)
 
% of subjects achieving a PtGA score of 0 or 1 and a <math>\geq 2</math> point reduction from baseline at Week 2, 4, 8, 12, and 16.
 

 
To evaluate the efficacy of RPT193 administered orally QD for 16 weeks to subjects with moderate-to-severe AD in subject subpopulations.
 
	
 
% change in EASI in the following subgroups:             
 
Prior treatment with dupilumab or tralokinumab (Yes or No)
 
Baseline EASI score of <math>< 21</math> or <math>\geq 21</math>
 
Baseline %BSA of AD affected skin <math>< 50\%</math> or <math>\geq 50\%</math>
 
Baseline vIGA score (3 or 4)
 
Age group
 
Race
 
Ethnicity
 
Pretreatment CCL17 levels
 
Pretreatment CCL22 levels.
 
 
 

 
Explore durability of treatment effect in those who have demonstrated an objective response at Week 16.
 
	
 
Proportion of subjects maintaining EASI-50 at Weeks 18, 20, 24 among those achieving an EASI-50 at Week 16 and not receiving rescue therapy from Week 8 to Week 16.
 
Proportion of subjects maintaining EASI-75 at Weeks 18, 20, 24 among those achieving an EASI-75 at Week 16 and not receiving rescue therapy from Week 8 to Week 16.
 
Proportion of subjects maintaining EASI-90 at Weeks 18, 20, 24 among those achieving an EASI-90 at Week 16 and not receiving rescue therapy from Week 8 to Week 16.
 
Proportion of subjects maintaining a vIGA score of 0 or 1 at Weeks 18, 20, 24 among those achieving a vIGA score 0 or 1 at Week 16 and not receiving rescue therapy from Week 8 to Week 16.
 


 
Explore the durability of the treatment effect after cessation of treatment at Week 16.
 
	
 
% change in EASI at Weeks 18, 20, and 24 compared to Week 16 among those not receiving rescue therapy from Week 8 to Week 16.
 
% change in SCORAD at Weeks 18, 20, and 24 compared to Week 16 among those not receiving rescue therapy from Week 8 to Week 16.
 

Exploratory (Pharmacokinetic)	

 
To evaluate the PK of RPT193 following administration of multiple oral doses of RPT193 administered orally QD for 16 weeks to subjects with moderate-to-severe AD.
 
	
 
PK parameters at Week 2, 4, 8, 12, 16, and 18.
 

### A. Estimand

The main estimands associated with the primary and key secondary endpoints to support regulatory decisions are described in the following table:

Attribute	Description
Treatment	RPT 193-02 (50mg, 200mg, 400mg) and Placebo
Population	Adult subjects with moderate-to-severe AD as defined by the inclusion/exclusion criteria
Endpoint	
Primary Endpoint
 
 
% change in Eczema Area Severity Index (EASI) from baseline at Week 16
 
 
Key Secondary Endpoints
 
 
% of subjects achieving a Validated Investigator Global Assessment (vIGA) score of 0 or 1 at Week 16
 
% of subjects achieving EASI-75, defined as a 75% reduction in EASI from baseline to Week 16
 
% change from baseline in PP-NRS from an itch daily e-Diary at Week 16.
 

Intercurrent Events	
 
Early termination of study treatment: Subjects who discontinue from the study treatment prior to Week 16 will be analyzed by the treatment policy strategy, i.e., all data collected after termination of study treatment but prior to rescue medication will be included in the analysis. Missing post discontinuation values will be imputed according to details provided below.
 
Use of rescue medications: Subjects who use rescue medication during the 16-week treatment period will be analyzed by the hypothetical strategy. All EASI/vIGA/PP-NRS scores collected after the start of rescue medication will be set to missing. The missing data after the use of rescue medication will be imputed to follow a similar profile as the placebo group.
 

Population-level Summary	
Primary Endpoint
 
 
Difference in mean percent change from baseline in EASI score between each RPT193 dose and placebo at Week 16.
 
 
Key Secondary Endpoints
 
 
Difference in percentage of subject achieving vIGA of 0 or 1 between each RPT193 dose and placebo at Week 16.
 
Difference in percentage of subject achieving EASI-75 between each RPT193 dose and placebo at Week 16.
 
Difference in mean percent change from baseline in PP-NRS
 

	between each RPT193 dose and placebo at Week 16.
--	--

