Study drug dosing daily at home ^k		X																					
Daily subject e-Diary for drug dosing at home		X																					
PK sampling – Blood ^l		X	X	X	X	X	X	X	X	X													
Tape stripping ^m		X	X	X	X	X	X	X	X	X													
Skin microbiome samples (swab) ⁿ		X	X	X	X	X	X	X	X	X													
Plasma Sample Collection for Biomarker Exploration ^o		X		X			X																
Serum cytokines/chemokines and biomarker levels		X	X	X	X	X	X	X	X	X													
Immunophenotyping – Blood ^p		X	X	X	X	X	X	X	X	X													

Visit	Screening	Baseline	Treatment (Day 1 to Day 113)						Follow-up (Day 127 to Day 169)				
			Day 15	Day 29	Day 57	Day 85	Day 113	Day 127/ET/Discon	Day 141	Day 169			
Study Day	Day -35 to -1	Day 1											
Week Number	Visit 1	Visit 2	Week 2	Week 4	Week 8	Week 12	Week 16	Week 18	Week 20	Week 24			
Window (day)			±2	±3	±3	±3	±3	±3	±3	±3			±3
Pharmacogenomics		X											
Cell Pellets ⁹													
Study drug distribution		X	X	X	X	X	X						
Study drug collection/review			X	X	X	X	X						
Rescue therapy collection/review (on or after Day 57 if applicable)					X	X	X		X	X		X	
Application of rescue therapy in e-Diary (if applicable)					X	X	X		X	X		X	
Prior and concomitant medication													
AE/SAE reporting	Ongoing from the time of signing the ICF (non-treatment and treatment-emergent adverse events)												
	Ongoing from screening												

Abbreviations: ACQ=asthma control questionnaire; ADSS=atopic dermatitis sleep scale; AE=adverse event; BMI=body mass index; BSA=body surface area;

DLQI=Dermatology Quality of Life Index; EASI=Eczema Activity and Severity Index; ECG=electrocardiogram; ET=Early Termination;

FSH=follicle-stimulating hormone; ICF=Informed Consent Form; PK=pharmacokinetics; POEM=Patient-oriented eczema measure; PP-NRS=Peak Pruritus

Numerical Rating Scale; PtGA=Patient’s Global Assessment; SAE=serious adverse event; SCORAD=SCORing Atopic Dermatitis; [REDACTED]

[REDACTED]: TB=tuberculosis; vIGA=Validated Investigator Global Assessment.

Baseline assessments to be obtained pre-dose.

There are no post-dose blood draws.

- Full physical examination at Screening, partial physical examination at all other visits.
- Height and weight will be collected, and BMI calculated at Screening. Weight will be collected at follow-up.
- Serum pregnancy test at Screening, and urine pregnancy test at other visits. Please see Appendix 11 for further details.
- A negative COVID-19 test is required at Screening (see also Section 8.9.2).

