6.6.2.5 Corticosteroids for Nose, Lungs, Eyes, and/or Ears

Intranasal corticosteroids and inhaled corticosteroids are allowed. Eye and ear drops containing corticosteroids are also allowed when used as directed.

6.6.2.6 *Herbals and supplements*

Subjects may take herbals and/or supplements with the following conditions. First, subjects taking herbals and/or supplements at screening who wish to discontinue these may do so provided that they do the following for the duration of the study: 1) continue to refrain from taking the herbal/supplement and 2) do not introduce a new herbal and/or supplement. Second, subjects who intend to continue taking herbal products or supplements during the trial must agree to continue the regimen documented at Screening throughout the study unless discontinuation is considered medically necessary.

6.6.3 **Prohibited Therapies or Procedures**

Female subject agrees not to have egg retrieval during the study and for 30 days after the last study drug administration.

Male subject agrees not to donate sperm during the study and for 90 days after the last study drug administration.

Table 3 lists prohibited medications that are not to be used from the defined washout periods before the first administration of study treatment at the Day 1 visit through the last study visit.

Subjects who start prohibited medications or therapies as a treatment for AD or other reasons during the study may be withdrawn from study treatment for safety reasons. If in any doubt, Investigators are advised to discuss medications with the Medical Monitor.

Table 3 Prohibited Therapies or Procedures for Study Duration with Washout Periods

Prohibited Medications, Products, and Procedures	Washout Period Prior to First Dose (Day 1)
Cell-depleting agent (e.g., rituximab)	6 months
Any marketed or investigational biological therapeutic (other than dupilumab)	16 weeks or 5 half-lives (whichever is longer)
Dupilumab	12 weeks
Oral investigational drugs	8 weeks or 5 half-lives of the investigational drug (whichever is longer)
Major elective surgical procedures	8 weeks
Systemic JAK inhibitors	8 weeks
Parenteral antibiotic	4 weeks
Live-attenuated vaccine (including but not limited to adenovirus-based COVID-19 vaccines such as the Janssen COVID-19 vaccine)	4 weeks
mRNA-based COVID-19 vaccines (Pfizer-BioNTech or Moderna)**	2 weeks

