6.6.4 Rescue Medications

Subjects who require topical corticosteroids, calcineurin inhibitors, or PDE4 inhibitor medications that could directly impact AD disease activity prior to Day 57 will be withdrawn from study drug and the study if requiring such topical therapies prior to Day 57.

Starting at Day 57, rescue medications for persistent, intolerable AD activity may be considered by the Investigator. Investigators must document evidence of continued active AD with EASI unchanged from or greater than the Baseline EASI score over 2 consecutive visits before initiating therapy. All subjects requiring rescue therapy between Day 57 (Week 8) and Day 113 (Week 16) will remain in the study and on study drug until Week 16.

After the end of treatment at Day 113 and during the follow-up phase, subjects may also initiate rescue if either the subject or investigator feels that there is persistent, intolerable AD activity.

Permitted rescue medications include low- to moderate-potency (class IV-class VII) topical corticosteroids ([Appendix 14](#)) and should be applied only to problem areas. A topical calcineurin inhibitor, topical PDE4 inhibitor (e.g., crisaborole), or low-potency topical steroid may be used on the face if affected. Subjects who require rescue therapy will be considered non-responders for all efficacy endpoints with data imputed for subsequent continuous endpoints for all time points as detailed in the Statistical Analysis Plan (SAP). Ideally, the specified medication for rescue treatment would be supplied by the clinic so that the tube could be weighed prior to administration. In addition, use of the specified medication should be recorded in the e-Diary, and the medication should be brought to clinic at subsequent visits to assess amount of medication used.

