7.2.1 Discontinuation

Subjects who discontinue the study after the first dose will be asked, if they agree, to come for a last assessment (ET/Discon visit). Subjects who are discontinued for safety reasons may be asked to come for additional follow-up visits, at the Investigator's discretion, after the ET/Discon visit to ensure appropriate medical care and AE follow-up.

Reasons for discontinuation include the following:

- The Investigator decides that the subject should be withdrawn for any of the following reasons, but not limited to: difficulties in obtaining blood samples, violation of the protocol, severe AEs or SAEs, or for any other reason relating to the subject's safety or integrity of the study data. If this decision is made because of a SAE, the study drug is to be discontinued in that subject immediately and appropriate measures are to be taken. The Investigator will notify the Sponsor immediately.
- The attending physician requests that the subject be withdrawn from the study.
- The subject, for any reason, requires treatment with another systemic therapeutic agent that has been demonstrated to be effective for treatment of the study indication (e.g., oral corticosteroids, dupilumab, tralokinumab oral calcineurin inhibitor, oral immunosuppressive). In this case, discontinuation from the study occurs immediately upon introduction of the new agent.
- The subject is lost to follow-up. In this case, a reasonable attempt to contact the subject and ascertain his or her status must be made, and these attempts must be documented.
- The subject becomes pregnant at any time during the study.
- A clinically significant change in a laboratory parameter occurs (See [Table 4](#)),
- Onset of an opportunistic infection during the study.
- Other: the subject may withdraw from the study for any other reason, including withdrawal of consent.

- The Sponsor or regulatory authorities, for any reason, stop the study. In this case, all subjects will be discontinued from the study. The Investigator will immediately, on discontinuance of the study by the Sponsor, in its entirety or at a clinical trial site, inform both the subjects and the Institutional Review Board/Research Ethics Board/Independent Ethics Committee (IRB/REB/IEC) of the discontinuance, provide them with the reasons for the discontinuance and advise them in writing of any potential risks to the health of subjects or other persons.

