## 2. Missing EASI, vIGA and PP-NRS

Missing data will be imputed for the primary and secondary endpoints, which includes the composite EASI score, vIGA and PP-NRS for the 16-week treatment period. Assessment after the use of rescue will be set to missing prior to any imputation. No imputation is planned for the follow-up period. The following missing data techniques will be utilized:

**Last Observation Carried Forward (LOCF):** All missing data up to Week 16 will be imputed by the last observed value carried forward for any subsequent missing values. For patients with only baseline value, the baseline value will be carried forward to Week 16. This will be applied to the continuous endpoints of composite EASI score and PP-NRS.

**Worst Observation Carried Forward (WOCF):** All missing data up to Week 16 will be imputed by the worst observed value carried forward for any subsequent missing values. For patients with only baseline value, the baseline value will be carried forward to Week 16. This will be applied to the continuous endpoints of composite EASI score and PP-

NRS.

**Treatment Failures (TF):** All missing binary endpoint data up to Week 16 will be imputed as failure. This will be applied to key secondary binary endpoints of EASI-75, responder and vIGA score of 1 or 0, and other secondary endpoints of EASI-50, EASI-90, at least 2-point reduction in vIGA, at least 3-point/4-point reduction PP-NRS.

**Observed Cases (OC):** No missing data will be imputed. All observed data will be included. To reiterate, data after the rescue medication will be set to missing.

**Multiple Imputation (MI) under MAR:** Missing continuous endpoints of EASI, and PP-NRS will be imputed using the multiple imputation (MI) with analysis of covariance (ANCOVA) model as the primary analysis for time-points at which no value is observed. MI will be performed under missing at random (MAR) assumption. The MI is a simulation-based approach where missing values are replaced by multiple Bayesian draws from the conditional distribution of missing data given the observed data and covariates, creating multiple completed data sets.

For the EASI assessment, all missing scheduled visits as outlined in the protocol will be imputed. For the PP-NRS assessment, all missing weekly visits will be imputed.

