## **G. Prior and Concomitant Medications**

Prior medications are defined as any medication that stopped before the date of the first dose of study drug. These medications will be recorded on both the "Prior Dupilumab and/or Tralokinumab Meds" and the "Prior and Concomitant Medications" eCRF form. Concomitant medications are defined as any medication that was ongoing or ended at the date of first dose, or any medication that started on or after the date of first dose. These medications will be recorded on the "Prior and Concomitant Medications" eCRF form.

All medications will be coded using the World Health Organization Drug Dictionary (WHO-DD) version B3 Global September 2021. Prior and concomitant medications will be summarized separately by Anatomical-Therapeutic-Chemical (ATC) level 4 classification and PT by treatment group and overall.

Medications that are indicated as rescue medications will also be summarized. Detailed information of rescue medications/procedures including duration of use and incidence of use will be summarized by topical and systemic groups. Kaplan-Meier (K-M) curves for time to first rescue use will be generated. The duration of use will be calculated based on the first start date and end date by topical and systemic groups. Missing dates will be imputed following Section IV.D.

All medications will be presented in a listing. A separate listing will be presented to include the rescue medications.

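### The primary estimand removes scores only after rescue medication, which the SAP does not define, so scores taken on other AD-active therapy can stay in as monotherapy data

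*SAP*

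**What the plan says.** Both estimands (protocol 9.4.2; SAP II.A) name two intercurrent events.

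- **Stopping study treatment** is handled by treatment policy: "all data collected after termination of study treatment but prior to rescue medication will be included in the analysis".
- **Rescue medication** is handled by the hypothetical strategy: "All EASI/vIGA/PP-NRS scores collected after the start of rescue medication will be set to missing". SAP IV.D.2 repeats this single trigger: "Assessment after the use of rescue will be set to missing prior to any imputation". In the control-based imputation, scores taken after study drug stopped but before rescue are restored once imputation is complete.

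The SAP does not say what rescue is. Section VII.G refers only to a label in the data: "Medications that are indicated as rescue medications will also be summarized". Protocol 6.6.4 lists topical agents only, available from Day 57, and the Schedule of Activities has a matching row: "Rescue therapy collection/review (on or after Day 57 if applicable". Concomitant medication has its own row, running from screening.

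Three protocol sections say what happens to subjects who take other AD therapy:

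- **6.6.3**, for anything in Table 3: "Subjects who start prohibited medications or therapies as a treatment for AD or other reasons during the study may be withdrawn from study treatment". The sentence goes on to give safety as the ground.
- **6.6.4**, for topical corticosteroids, calcineurin inhibitors or PDE4 inhibitors needed early: such subjects "will be withdrawn from study drug and the study if requiring such topical therapies prior to Day 57".
- **7.2.1**, for a systemic agent effective in AD, needed for any reason, with oral corticosteroids among the examples: "discontinuation from the study occurs immediately upon introduction of the new agent".

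**The concern.** The trial asks about RPT193 as monotherapy, and the sponsor has chosen to remove scores affected by added AD treatment. That choice works only if the rule catches the treatments that matter. As written it catches whatever carries a rescue label and nothing else.

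Unlabelled therapy is foreseeable. ACQ-5 is collected in subjects with asthma, and only uncontrolled moderate-to-severe asthma is excluded, so an oral steroid course for an exacerbation can occur. It would not be AD rescue. Table 3 prohibits topical JAK inhibitors and phototherapy, but neither is on the 6.6.4 rescue list or among the 7.2.1 examples. At stake is whether an EASI measured on such therapy is credited to the randomized arm. Placebo scores carry extra weight, because the control-based imputation fills gaps in every arm from observed placebo data.

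**Working it through.** **1. The plan's own figure (background only).** 60 / (1 − 0.10) = 66.7, rounded up to 67 per group; 4 × 67 = 268, which matches SAP III.C. The protocol's approximately 265 is close. The base of 60 cannot be rebuilt because the effect size, SD and power are redacted. The concern does not rest on this figure.

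**2. Tracing cases through the rules.**

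| Therapy started | Protocol sections that apply | Rescue under the SAP? |
|---|---|---|
| Oral corticosteroid for asthma | 6.6.3 (permissive) and 7.2.1 (mandatory) | Nothing makes it so |
| Topical JAK inhibitor | 6.6.3; not a 6.6.4 topical, not a systemic agent under 7.2.1 | Nothing makes it so |
| Phototherapy | 6.6.3; not on the 6.6.4 list or among the 7.2.1 examples | SAP VII.G mentions rescue procedures; the estimand names medication only |
| Systemic therapy for AD | 6.6.3 and 7.2.1 | Unsettled: VII.G expects a systemic rescue group, 6.6.4 permits none |
| Topical corticosteroid before Day 57 | 6.6.3 and 6.6.4 | Unsettled: covered under the rescue heading, but before rescue begins |

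**3. When an unflagged case reaches the Week 16 result.**

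- *Kept on study, as 6.6.3 allows.* The EASI on Days 99 to 119 is observed on the added therapy and used as it stands. PP-NRS for Week 16 is the average over Days 107 to 113, and those diary entries stay too.
- *Withdrawn, with an ET/Discon visit.* SAP IV.C assigns scores by actual study day, so the EASI and vIGA count at Week 16 only if the visit falls on Days 99 to 119. An earlier ET/Discon score is restored after imputation, so on the natural reading it does not drive that subject's imputed Week 16 value.

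**4. Size, on assumed inputs.** Let fP and fT be the shares of placebo and active subjects whose Week 16 EASI is taken on unflagged AD-active therapy. Let B be the improvement in percent change that the therapy adds, relative to the value the hypothetical strategy would use. Then

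shrinkage of the treatment difference = B × (fP − fT).

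| B (points) | fP, fT | Shrinkage (points) |
|---|---|---|
| 20 | 5%, 2% | 20 × 0.03 = 0.6 |
| 20 | 10%, 5% | 20 × 0.05 = 1.0 |
| 35 | 10%, 5% | 35 × 0.05 = 1.75 |
| 50 | 15%, 5% | 50 × 0.10 = 5.0 |
| any | equal | 0 |

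If use were heavier on active drug, the sign would reverse and the difference would be inflated.

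For scale, take 60 per group, two-sided 0.05 and an assumed SD of 40. The standard error is 40 × √(2/60) = 7.30. The detectable difference is 7.30 × (1.960 + 0.842) = 20.5 points at 80% power and 7.30 × (1.960 + 1.282) = 23.7 at 90%. A 1-point shrinkage lowers power from 80% to about 76%, or from 90% to about 87%. A 5-point shrinkage lowers it to about 56% or 73%. For SDs of 30 to 45 the detectable difference runs from 15.3 (80% power) to 26.6 (90% power).

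**The case against.** The strongest reply is that the protocol largely prevents the problem. Uncontrolled moderate-to-severe asthma is excluded, and an oral steroid triggers immediate study exit under 7.2.1. At most one on-therapy visit should then follow, and it counts at Week 16 only within Days 99 to 119. The per-protocol set may drop such subjects, and the MMRM discards data after study withdrawal. Keeping data under other concomitant therapy is also a legitimate treatment-policy choice.

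Much of this stands as a limit on size. It does not close the gap. Section 6.6.3 leaves room to keep a subject, and for topical JAK inhibitors and phototherapy no mandatory exit rule clearly applies. The per-protocol and MMRM analyses are sensitivity analyses only. Treatment policy for these therapies would be defensible if stated, but the plan names no strategy for them, and keeping them sits oddly beside removing scores after permitted topical rescue.

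A reader might also infer three stronger things that the documents do not support:

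- *That 6.6.3, 6.6.4 and 7.2.1 contradict each other three ways.* Sections 6.6.4 and 7.2.1 cover different therapies and are compatible. Each is in tension only with 6.6.3, which concerns study treatment, on safety grounds, and does not say whether the subject stays in the study.
- *That systemic therapy for AD is certainly retained while mild topicals are removed.* SAP VII.G plans to summarize rescue in topical and systemic groups, so such use may be flagged.
- *That early topicals certainly escape the rule.* The SAP rule spans the whole 16 weeks, and 6.6.4 deals with these topicals under its rescue heading. A subject withdrawn before Day 57 would also seldom have a score near Week 16.

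**Conclusion.** The concern holds in this form: the second intercurrent event is tied to an undefined label, and AD-active therapy outside that label stays in the primary analysis by default. Early topicals and systemic therapy for AD are undetermined; the SAP does not settle whether they count.

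The size is unknown. The 0 to 5 point range rests wholly on assumed usage and effect, and it assumes that every counted subject has an on-therapy Week 16 score, which withdrawal under 6.6.4 or 7.2.1 would often prevent. Bias toward no effect is a tempting conclusion but follows only if use is heavier on placebo; asthma steroids, for one, need not track AD control. This should be corrected before unblinding because it is cheap to do. There is no evidence that it would overturn the result.

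**What to change.** In SAP II.A and IV.D.2, define the second intercurrent event as the start, on any day up to Week 16 and for any indication, of rescue medication or of a prohibited therapy expected to improve AD. The list would be:

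- systemic corticosteroids or immunosuppressants;
- systemic or topical JAK inhibitors;
- biologics;
- phototherapy;
- topical corticosteroids, calcineurin inhibitors or PDE4 inhibitors.

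Exclude what the protocol permits, such as anti-infectives under 6.6.2.2 and inhaled, nasal, eye or ear corticosteroids under 6.6.2.5. Pointing to all of Table 3 would be too broad: it lists topical antimicrobials, which 6.6.2.2 allows for acute infection.

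Identify the event from concomitant-medication records (and concurrent-procedure records for phototherapy), using a coded list fixed at the blinded data review. Set later EASI, vIGA and PP-NRS scores to missing, including at ET/Discon, do not restore them, and impute as for rescue.

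The cost is SAP wording, one coding list and a few more imputed values. No new data are needed, and SAP I.B allows changes until unblinding.

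Separately, the sponsor must reconcile the permissive wording of protocol 6.6.3 with the mandatory study withdrawal in 6.6.4 and 7.2.1. Which clinical rule applies is for the sponsor to decide; no view is taken here.
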